Population and Setting: We will randomize up to 250 MVAHCS patients in a ratio of 2:1 intervention: control. Inclusion Criteria (EHR):

- 1) Adults >=18 participating in care, defined as a primary care or pulmonary visit within the past 2 years.
- 2) Past-year smoking status in the electronic health record defined by health factors indicating current smoking (Via validated VA algorithm)
- 3) ICD-10 diagnoses of COPD within the past 2 years
- 4) Not already enrolled in VA tobacco treatment (pharmacist treatment, tobacco groups, mental health tobacco treatment). Patients taking only tobacco cessation medications without counseling will be included.
- 5) Not enrolled in hospice
- 6) No diagnosis of advanced dementia

Exclusions (phone eligibility assessment):

- 1) Unable to communicate by phone in English
- 2) No text-capable phone
- 3) Already guit smoking
- 4) Already participating in tobacco treatment program (note: if using OTC meds without counseling, will not be excluded)
- 5) Decline to be in study but would prefer to receive care coordination immediately

Eligibility, Sampling and Recruitment: We will screen and enroll patients who meet the eligibility criteria, applying the above criteria initially using the EHR, confirming criteria during phone contact. Patients will be randomized irrespective of their intention to quit smoking.

Women and Racial Minorities: To increase representation of these groups, we will oversample eligible women and racial/ethnic minority patients with a goal of 14% female patients and 24% minority patients invited to participate.

Study Procedures:

[figure not shown]
Screening: Research coordinator will screen patients for possible eligibility using a secure electronic application located behind the VA firewall.

Invitation: Study is minimal risk and will be conducted under a waiver of HIPPA and documentation of informed consent. Eligible participants will be sent an "opt out" letter that describes the study and contains the necessary elements of informed consent. Eligible patients will have the opportunity to opt out at this time by calling the study team.

Recruitment: Patients will be recruited by phone starting 1 week after letter is

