- Tobacco cessation class with pharmacist co-management
- Pharmacist tobacco clinic
- Quitline with primary care or pharmacist medication management
- Stay Quit Coach App or SmokeFreeVet texting (VA tobacco treatment programs) and primary care medication management

For participants still unwilling to enroll in treatment, they will be offered a stress relief program and can request a one-time callback in a month.

Once the participant has elected which program they would prefer, study staff will place the appropriate referral within CPRS, addending the research participant note to document the selection and discharging the participant from the Annie protocol.

- Pharmacist: Direct co-signature to PACT pharmacist in CPRS
- Cessation class or PCMI: notification to [name], tobacco lead clinician
- Quitline + primary care medication management: notification to [name] (Tobacco Lead Clinician)+ documentation that patient consents to guitline call + co-signature notifying PCP
- Direct enrollment in SmokeFreeVet on smokefree.gov website
- Assistance with downloading of StayQuit Coach

Patients who select to enroll in treatment will be called in approximately a month to ensure they have connected with care and have no further questions.

Final Survey, Biochemical Confirmation of Abstinence, and Qualitative Assessment:

Survey: All participants will be surveyed 6 months after randomization to determine participation in any tobacco treatment (primary outcome), current self-reported tobacco use, quit attempts, and acceptability and feedback of the texting program. Completion via phone will be prioritized but participants will be provided the option to complete the survey via Qualtrics link via email or paper copy. Participants will be contacted 3 times via phone. If they are unable to be reached, they will be sent a letter encouraging them to call the study team to complete the survey.

EHR: Data will be pulled from the CDW supplemented by limited chart review to identify: prescriptions for tobacco-cessation medications, tobacco-treatment-related visits. Tobacco treatment visits will be identified by combining ICD-10 codes for tobacco use and treatment with note titles and visit types for pharmacists, psychologists, and primary care providers.

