Cost Analysis: We will prospectively capture information on cost associated with performing the proactive tobacco treatment intervention. To estimate the cost associated with implementation, we will capture time spent building any templates and electronic tools, and training staff. To estimate cost associated with staffing the program once it is created, for one month during the pilot, all study staff will enter daily the time spent in the clinical tasks associated with delivering the intervention into a spreadsheet, excluding activities that are related only to research administration. To estimate cost related to an increase in use of tobacco treatments attributable to the program, we will estimate the difference in use of tobacco treatments in addition to the intervention-related costs.

Measurements and Data Source:

See Table 1 for full list of measurements and data sources.

Table 1: Measures	
Measures	
Baseline Measures	
Survey	Demographics: Age, gender, race, ethnicity, education, income, health literacy Health Measures: Self-reported health, respiratory symptoms questionaire, diagnosis of COPD, Audit-C Access to Technology: Access to devices, access to internet, use of e-mail, use of secure patient portal, frequency of texting, electronic health literacy scale Tobacco Measures: current tobacco product use, heaviness of smoking index, past-year quit attempts and use of cessation resources, ever use of cessation resources, quit confidence scale, motivation to quit, intention to quit

EHR	Charlson comorbidity index, mental health diagnoses	
Outcome Measures		
Study Recorded and EHR	Response to the program (via telephone, via Annie App), timing of response to program, Acceptance of referral, choice of referral program, cessation medications (varenicline, bupropion,	
ENK	nicotine replacement single/combination), documented tobacco treatment visits (pharmacist, class, mental health, primary care) or warm handoff to quitline	
Survey	Primary outcome: Use of any tobacco treatment	
	Secondary Outcomes: Use of combination treatment (behavioral + pharmacotherapy), individual	
	treatment choice (program, medications), heaviness of smoking, quit attempts (y/n and number),	
	7 day and 30 day abstinence, Stage of change, quit confidence	
	Additional Outcomes: Acceptability of text messaging program, feedback on messages,	
	agreement to qualitative interview	

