A sample size of approximately 167 participants in the intervention arm will be sufficient to estimate rates of contact, referral, and enrollment in behavioral and pharmacologic treatment with a precision (standard error) of +/- 3.9% and the control arm of 5.4%, which will be informative for planning future research. However, if feasible we will continue recruitment to attain more precision. Similarly, we will be able to estimate eligible population sizes, outreach connection rates, referral rates, rates of behavioral treatment enrollment and rates of pharmacologic treatment separately, and related facets of the intervention delivery to within similar degrees of precision. We will have enough variation in patient characteristics to stratify uptake on key variables, including age and disease severity. We may not have sufficient power to determine a statistically significant increase in enrollment in behavioral and pharmacologic treatment or smoking cessation, but these will be examined as aims of future research.

Cost Analysis: Estimates of time and workload for each staff member and clinical role involved in implementing and staffing the program will be combined with regional VA salary information to generate total costs for the proactive program. We will combine this also with regional estimates of pharmacy costs and the prevalence of

COPD and tobacco use at the MVAHCS to produce an overall estimate of cost for the program should it be implemented for the total population.

Qualitative Analysis: Transcribed interviews and notes will be analyzed using directed content analysis with NVIVO software, with constructs based on the technology adoption model and the consolidated framework for implementation research.

Expected Outcomes and Deliverables:

We expect that an electronic proactive patient engagement program will be feasible and will result in more patients enrolling in tobacco treatment. We also expect variation in response to the program by age and baseline technology use. We expect to find that the budget impact of the intervention itself is small and that most of the increase in cost will be due to increased utilization of existing quit resources.

Informed Consent

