There is no cost to participate in this study.

Subject Compensation

Participants will be paid \$20 per survey for a total of \$40 to be paid at the completion of the follow up survey. The subset of participants who participate in the interview following the completion of the intervention will be paid \$30 for their time. Subjects will be paid \$30 for providing biochemical confirmation. Participants will not be compensated for participation in the text messaging program. Participants will be asked if they already participate in EFT. For those not participating, they will be sent the EFT paperwork in the mail after they consent to be in the study. This will include all EFT paperwork, a letter explaining how to complete the paperwork, and a return address envelop for returning the paperwork to study staff. Study staff will scan and send via an encrypted email the EFT paperwork to the Agent Cashier office. In the 5th month of study, study staff will confirm EFT paperwork have been completed correctly and resend the EFT paperwork if it has not.

Project Management and Research Team Coordination:

As PI, [name] will lead all activities related to the study, in collaboration with co-investigators and the research coordinator.

Data and Safety Monitoring Plan

The proposed research will be overseen by the Minneapolis VA IRB. The PI will be responsible for monitoring safety, minimizing risks related to data and safety, protecting the confidentiality of subject data, and reviewing and reporting adverse events and unanticipated problems to the IRB.

The principal investigator will review reports of adverse events and unexpected problems during the conduct of the research. The principal investigator will report all adverse events including breach of confidentiality to the MVAHCS IRB. The principal investigator will ensure that any IRB recommendations and actions related to monitoring are enacted.

Data will be maintained in accordance with MVAHCS protocols. Electronic information will be housed behind the VA firewall and physical files will be kept within locked file cabinets in locked offices. We are applying for a waiver of HIPPA and waiver of documentation of informed consent. Other patient identifiers will be kept in the separate crosswalk.

References:

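### Does the stated precision of 3.9% and 5.4% fail because the primary outcome comes from a 6-month survey with no allowance for non-response?

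*Combined protocol and SAP*

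**What the plan says.** Population and Setting sets the size: "We will randomize up to 250 MVAHCS patients in a ratio of 2:1 intervention: control". Power and Sample Size then relies on "A sample size of approximately 167 participants in the intervention arm", which is two thirds of 250, so nobody is discounted for missing follow-up. It states that rates of contact, referral and enrollment in treatment will be estimated "with a precision (standard error) of +/- 3.9% and the control arm of 5.4" percent. The rate behind these figures and the control-arm number are not given. The same section accepts that power to show an increase in treatment enrollment or cessation may be lacking.

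Under Final Survey: "All participants will be surveyed 6 months after randomization to determine participation in any tobacco treatment (primary outcome"). The Survey row of Table 1 agrees: "Primary outcome: Use of any tobacco treatment". Follow-up effort is described: "Participants will be contacted 3 times via phone", then a letter, with online and paper options. Survey payment is "to be paid at the completion of the follow up survey".

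Treatment use is also captured without the survey. The EHR paragraph plans a data-warehouse pull of cessation prescriptions and treatment visits. The Study Recorded and EHR row of Table 1 lists cessation medications and "documented tobacco treatment visits (pharmacist, class, mental health, primary care) or warm handoff to quitline" among the outcome measures.

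The Analysis Plan will report the rate of receipt of any treatment, with a 95% confidence interval, in each arm. It does not say whether the denominator is survey completers or all randomized.

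**The concern.** The sample-size justification uses every randomized participant, while the outcome labelled primary needs a survey answer six months later. If a fifth or more do not answer, fewer observations support that rate than the precision statement implies.

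The counting of non-responders could matter more than the precision. Leaving them out, treating them as untreated, or filling them in from the health record would give different rates. The weighting in the Analysis Plan corrects for sampling by gender and race, not for non-response. The Withdrawal of Subjects section adds some doubt: participation may end when a person cannot be contacted, and data collection stops after withdrawal. Those who cannot be reached are the people for whom the record would be the only source.

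At stake is whether the pilot's treatment rates, which are meant to inform a larger trial, are as precise and as clearly defined as they appear.

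**Working it through.** **Inputs.** Up to 250 randomized at 2:1, so about 167 and 83 (Population and Setting; Power and Sample Size). Printed standard errors 3.9% and 5.4%. Nearest treatment rate in the document: 15% receiving cessation medication within 90 days of discharge (Scientific Rationale). This is an imperfect proxy, covering medication only in a hospitalized cohort. Survey completion of 70% or 80% is assumed, as is any treatment rate other than 15%.

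**Formula.** SE = √(p(1−p)/n).

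**Reproducing the plan's figures, with p = 0.5 inferred.**
- n = 167: √(0.25/167) = 3.87%, printed as 3.9%.
- n = 83: √(0.25/83) = 5.49%, which rounds to 5.5%, not 5.4%.
- n = 165 and 85: 3.89% and 5.42%, which round to both printed figures.

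The control figure is therefore off in the last digit at most.

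**Precision of a rate among survey completers.**

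| Treatment rate | 80% complete (134/66) | 70% complete (117/58) |
|---|---|---|
| 50% | 4.32% / 6.15% | 4.62% / 6.57% |
| 30% | 3.96% / 5.64% | 4.24% / 6.02% |
| 20% | 3.46% / 4.92% | 3.70% / 5.25% |
| 15% | not needed | 3.30% / 4.69% |

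At 50% with 80% completion, the increase over full follow-up is 4.32 − 3.87 = 0.45 points and 6.15 − 5.49 = 0.66 points. The 95% half-widths go from 7.6 to 8.5 points and from 10.8 to 12.1 points. At 30% with 80% completion, the excess over the printed figures is 3.96 − 3.9 = 0.06 and 5.64 − 5.4 = 0.24 points. At 20% or below, both arms stay within the printed figures at either completion rate.

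**Effect of the counting rule, illustrative, with 20% treated among completers.**
- If non-responders are treated at half that rate, a completers-only rate exceeds the all-randomized rate by 0.20 − (0.8×0.20 + 0.2×0.10) = 2 points at 80% completion, and by 0.20 − (0.7×0.20 + 0.3×0.10) = 3 points at 70%.
- With nothing known about non-responders, the all-randomized rate lies between 0.8×0.20 = 16% and 16% + 20% = 36% at 80% completion, and between 0.7×0.20 = 14% and 14% + 30% = 44% at 70%.

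The second pair is a worst case that ignores the planned prescription and visit data. The half-rate in the first has no source in the document.

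**What the precision sentence covers.** Contact and referral are recorded by study staff. Prescriptions and treatment visits come from the data warehouse. Neither needs a completed survey, so the full randomized number is a fair denominator for these quantities.

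**The case for a change.** The strongest case for a change is that the Analysis Plan makes estimation of these rates its primary focus, and receipt of any treatment is one of them. A reader cannot tell whether the slack from assuming about 50% is real, because neither the rate nor the completion is stated. At a 30% rate and 80% completion it is already used up. Writing down the denominator before analysis would also prevent a choice made after seeing the data, at the cost of a few sentences. Adding a supportive estimate that counts treatment found in either the survey or the record, among all randomized, would use data already being extracted.

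Much of this is true as description. The denominator is unwritten, and no rule covers a participant with record data but no survey.

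It does not carry the case for change. The supportive estimate would leave the primary result where it is and could not replace it. In non-responders the record would miss over-the-counter, non-VA and app or texting treatment. It might also miss them unequally by arm, since study staff place and document referrals in the record for intervention participants. The withdrawal point shows no contradiction: the bar on further collection is tied to a participant's own withdrawal, and nothing says that a missed survey stops the record pull.

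**Conclusion.** No change is needed. No printed figure is materially wrong: the standard errors are near-worst-case values for about 250 randomized, with a last-digit slip in the control arm if its size is 83. They stand for contact, referral and record-based treatment enrollment. For the survey-based rate they hold at 15% to 20% treated with 70% completion, and they are exceeded by a few tenths of a point at 30% with 80% completion. At 50% with 20% non-response, they rise by about 0.5 and 0.7 points over full follow-up. The plan sets no go/no-go threshold on these values and claims no power for treatment differences, so a shift of that size changes no decision.

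What remains is missing detail on the denominator and on non-responders. An analyst would ordinarily report the survey rate with its number of respondents and show the record-based medications and visits that Table 1 already lists. This conclusion rests on assumed completion of 70% to 80% and on treatment rates that the plan does not state. Much lower completion together with a rate near 50% would widen the survey-based interval further: at 60% completion (100/50) the standard errors would be 5.0% and 7.1%. The record-based estimates would be unaffected.
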